13.1.3. Presentation of Pharmacokinetic Results

Listings of PK blood sample collection times, derived sampling time deviations, drug concentrations, and PK parameters will be provided by subject in the PK population.

Plasma concentrations for lenalidomide will be summarized by nominal time points or collection intervals, including sample size (N), mean, StdDev, % coefficient of variation (CV%), geometric mean, geometric CV%, minimum, median, and maximum. Mean (\pm StdDev) and

individual plot of lenalidomide plasma concentrations versus time will be presented in both linear scale and semi-logarithmic scale.

PK parameters will be summarized descriptively (N, mean, StdDev, CV%, geometric mean, geometric CV%, minimum, median, and maximum) by age class (1 to < 6, 6 to < 12 and \geq 12 years) and overall.

13.1.4. Population Pharmacokinetic Analysis

Lenalidomide concentration data from this study will be combined with the concentration data from other pediatric studies and literature data to perform a population pharmacokinetic analysis. Main pharmacokinetic parameters in plasma to be estimated include AUC, C_{max} , apparent clearance, and apparent volume of distribution. Effect of age and body size on lenalidomide PK will be assessed. Other relevant covariates for the main PK parameters may be identified. The between-subject variability for PK parameters will be estimated. If data allow, main PK parameters (clearance and volume of distribution) will be summarized by age as appropriate (eg, 1 to < 6, 6 to < 12, and \geq 12 years).

This analysis is not within the scope of this SAP and report, as it will be documented in a separate report.

14. INTERIM ANALYSIS

Periodic reports (at least semi-annually) will be provided to an external data monitoring committee (DMC). The first DMC meeting will be held after 4 subjects have completed at least 1 cycle of study treatment, if having not stopped therapy earlier due to a safety issue, in order to evaluate safety and provide a recommendation.

An interim analysis is planned to take place, at the end of Stage 1, once the first 18 subjects evaluable for the primary endpoint have been accrued and completed up to 4 cycles of lenalidomide treatment if they have not stopped therapy before 4 cycles, ie, the RR population. The interim analysis will assess the number of subjects with CR or CRi under lenalidomide treatment. If fewer than 3 of 18 subjects achieve a response then the study will be closed; otherwise the study shall continue as planned and enrollment shall continue into Stage 2.

At the interim analysis, only a subset of the summary outputs detailed in this SAP will be produced. No figures and listings will be provided, with the exception of AE listings. These summaries will include: analysis populations, subject disposition, demography and baseline characteristics, concomitant medications and procedures, morphological complete response rate within the first four cycles of treatment, overall response rate, summary of disease assessment outcome, summaries on exposure to lenalidomide, TEAE, TEAE with CTCAE grades 3 or 4, TEAE with CTCAE grade 3 or 4 related to lenalidomide, TEAE with CTCAE grade 5, cause of death during treatment period and cause of death after 28 days of end of treatment.

Should the study stop after Stage 1 then the primary final analysis will take place.

15. PRIMARY AND END OF STUDY FINAL ANALYSES

All tables, listings and figures detailed in this SAP will be provided for the primary final analysis that will be conducted when all on treatment subjects will have completed their Cycle 4 Day 28 assessments or will have met discontinuation criteria, whichever occurs first.

For the end of study final analysis, all outputs will be rerun once all subjects will have discontinued the follow-up period (up to 5 years after the last subject first dose of lenalidomide).

16. Changes to the Statistical Analyses Section of the Protocol

Denominator of the ORR rate will be defined as the number of subjects starting the cycle of interest instead of the number of subjects completing the cycle of interest as stated in the protocol.

Correlation will be computed between response and laboratory results obtained at baseline, instead of correlation between response and laboratory results at diagnosis and relapse as stated in the protocol.

The IWG response criteria in this study was brought in line with the actual criteria, ie. 'Progressive Disease' was replaced with 'Treatment Failure'.

Time to response endpoint was added as a secondary endpoint.

During the course of the study, due to a low (1 or fewer) number of subjects reporting certain measurements or to redundant presentation, it was determined that the analyses listed below would not be conducted:

- Summaries of prior cancer history, prior procedures/surgeries, procedures for prior cancers not under study and radiation treatment for prior cancers not under study.
- [REDACTED]
- Correlation between response with baseline/screening peripheral white blood cell count, absolute blast count, cytogenetics, [REDACTED]
- [REDACTED]
- Summary of durable response rate.
- AE summary tables for (treatment-emergent adverse events leading to death, SAEs related to lenalidomide, SAEs leading to discontinuation, Grade $\frac{3}{4}$ TEAEs by maximum intensity.
- Summary for AE of special interest related to lenalidomide, SAEs of special interest related to lenalidomide or leading to discontinuation of lenalidomide. AEs of special interest by maximum intensity.
- Second primary malignancy related tables, listings and figures.
- [REDACTED]
- Population PK analysis.

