1.3.2. Lenalidomide Pharmacokinetics

1.3.2.1. Pharmacokinetics in Pediatric Populations

The pharmacokinetics (PK) of lenalidomide have been evaluated in pediatric patients with solid tumors in two Phase 1 pediatric studies (Berg, 2011; Warren, 2011). A total of 47 pediatric patients were evaluated for PK in the two studies, with ages ranging from 4 to 21 years old. Doses studied were 20 to 116 mg/m²/day for children with brain tumors, 15 to 70 mg/m²/day for children with solid tumors, and 5 mg/m²/day for children with MDS. In these pediatric patients, plasma lenalidomide exposure (AUC and C_{max}) increased approximately proportional to dose. The median time to reach the maximum concentration in plasma was approximately 1 to 4 hours following the oral administration and the mean terminal half-life (t_{1/2}) of lenalidomide was 2 to 3 hour in the two studies. These observations are consistent with those historically observed in adult patients with hematological malignancies including AML.

In pediatric patients ≥ 5 years of age, preliminary population PK analysis suggests that body weight is positively correlated with lenalidomide clearance and volume of distribution, but age has no effect.

The relationship between lenalidomide apparent total clearance (CL/F) and body size (weight or body surface area [BSA]) is not available for children younger than 5 years. Because gastrointestinal (GI) and renal functions reach the adult level by 1 year of age, oral absorption and renal elimination of lenalidomide is not anticipated to be highly age-dependent in patients 1 to 5 years. However, effects of the growth-dependent changes in the body size on lenalidomide clearance (plasma exposure) and volume distribution is expected in the 1 to < 5 year-old age group of pediatric patients. The impact of growth on plasma lenalidomide exposure has been taken into account when considering the weight-based dose for this study.

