3.2. Secondary Endpoints

- Durable response rate.
- Duration of response (DoR).
- Disease assessment outcomes and overall response rate (ORR).
- Rate of hematopoietic stem cell transplant (HSCT).
- Incidence and severity of treatment-emergent adverse events (TEAEs).
- Rates of acute and chronic graft-versus-host disease (GVHD).
- Plasma pharmacokinetic (PK) parameters including lenalidomide apparent clearance and volume of distribution.
- Correlation of peripheral white blood cell count, absolute blast count and cytogenetics with response to lenalidomide.

[REDACTED]

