10.10. Pharmacokinetic Analysis

Approximately 50% of subjects should be younger than 12 years of age to provide adequate PK data for this age subset. Lenalidomide concentration data from this study will be combined with the concentration data from other pediatric studies and literature data to perform a population pharmacokinetic analysis. Main pharmacokinetic parameters in plasma to be estimated include AUC, C_{max} , apparent clearance, and apparent volume of distribution. Effect of age and body size on lenalidomide PK will be assessed. Other relevant covariates for the main PK parameters may be identified. The between-subject variability for PK parameters will be estimated. If data allow, main PK parameters (clearance and volume of distribution) will be summarized by age as appropriate (eg, 1 to < 6, 6 to < 12, and 12 to \leq 18 years).

Non-compartmental PK parameters in plasma may also be estimated using intensive lenalidomide concentration data collected from this study.

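### SAP section 16 lists population PK as not conducted, against SAP 13.1.4 and Protocol 10.10; taken literally, no specified analysis would assess body size

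*SAP*

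**What the plan says.** Protocol 3.2 has as a secondary endpoint: "Plasma pharmacokinetic (PK) parameters including lenalidomide apparent clearance and volume of distribution". Protocol 10.10 sets out how it is to be obtained: "Lenalidomide concentration data from this study will be combined with the concentration data from other pediatric studies and literature data to perform a population" PK analysis. The same section commits that "Effect of age and body size on lenalidomide PK will be assessed", and leaves the non-compartmental route optional: "Non-compartmental PK parameters in plasma may also be estimated using intensive lenalidomide concentration data collected from this study".

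SAP 13.1.4 repeats the population plan, including age and body size, and then adds: "This analysis is not within the scope of this SAP and report, as it will be documented in a separate report".

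SAP section 16, which lists departures from the protocol, includes population PK among analyses of which it says "it was determined that the analyses listed below would not be conducted". One reason covers the whole list: too few subjects with the measurement (one or none), or redundant presentation. The section does not say which reason belongs to which item.

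Within the SAP itself, 13.1.2 derives CL/F as dose over AUC to infinity and Vz/F as CL over the terminal rate constant. Under 13.1.3, "PK parameters will be summarized descriptively" in three age classes (1 to <6, 6 to <12, and 12 years and over) and overall. No normalisation by weight and no covariate analysis is specified.

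**The concern.** SAP 13.1.4 and section 16 cannot both stand: one promises a separate report, the other says the work will not be done. A reader who follows section 16 would find no analysis of body size anywhere in the plan.

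That matters because the protocol treats body size as the open PK question. Protocol 1.3.2.1 says that the relationship between CL/F and weight or body surface area "is not available for children younger than 5 years", and it expects growth to affect clearance and volume in the 1 to <5 group. Sections 7.1 and 10.10 steer about half of enrolment below 12 years for the sake of PK. Children would then be enrolled and sampled for a question that has no planned analysis.

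**Working it through.** **The plan's own figure.** The documents give no sample size or precision target for PK. The only stated size is the Simon design (continue with at least 3 of 18, succeed with at least 8 of 43). Summing P(X1 = x) × P(X2 ≥ 8 − x) over x ≥ 3, with X1 from 18 and X2 from 25 subjects, gives 0.0480 at a 10% response rate and 0.8003 at 25%. The design reproduces. It matters here only because it sets n = 18 or 43.

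**Ground 1: one or fewer subjects.** Protocol 6.26.1 samples every subject, 5 times at 20 kg or less and 7 times above.
- Stage 1: 18 × 5 = 90 to 18 × 7 = 126 planned concentrations.
- Both stages: 43 × 5 = 215 to 43 × 7 = 301.
- With half of the subjects under 12, the chance of one or none among 18 is (1 + 18)/2^18 = 0.00007.

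The planned model also pools other studies. The number of subjects with usable PK data is not in the documents, but this ground does not fit the sampling plan.

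**Ground 2: redundant presentation.** SAP 13.1.4 had already put population PK outside this report, and non-compartmental analysis also yields CL/F and Vz/F. Redundancy could therefore explain a missing output here. It does not explain an analysis left undone, and nothing else in SAP section 13 duplicates the body-size assessment.

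**Size of the body-size effect, from Protocol Table 1.** CL/F per kg = 2 mg/kg ÷ predicted AUC, that is 2000/AUC in L/h/kg:
- 1 to <2 years: 2000/3029 = 0.660
- 2 to <3 years: 2000/3461 = 0.578
- 3 to <4 years: 2000/3855 = 0.519
- 4-5 years: 2000/4420 = 0.452
- 6-11 years: 2000/5871 = 0.341

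The first four bands all fall in the SAP's class 1 to <6. The fall inside that class is 1 − 3029/4420 = 31.5%. The fall to 6-11 years is 1 − 3029/5871 = 48.4%. Both use the youngest band as base. A child of 35 kg or more reaches the 70 mg cap and receives less than 2 mg/kg, so 0.341 is if anything too high.

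Absolute CL/F moves the other way. With assumed weights of 10-12 kg at 1 to <2 years and 16-20 kg at 4-5 years, it is 6.6-7.9 and 7.2-9.0 L/h. A 12-18-year-old at the cap has 70,000/5988 = 11.7 L/h. A table of un-normalised CL/F by age class would show a rise that mixes growth with age.

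**What a weight regression could deliver.** For log CL/F on log weight alone, slope SE = s/(SDw × √(n − 1)). Assume s = 0.28, in line with Table 1's AUC CVs of 24.9-32.7%, and SDw, the SD of log weight, between 0.4 and 0.7:
- n = 18: 0.28/(0.4 × 4.12) = 0.17 to 0.28/(0.7 × 4.12) = 0.10
- n = 43: 0.28/(0.4 × 6.48) = 0.11 to 0.28/(0.7 × 6.48) = 0.06

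Adding age inflates the SE by 1/√(1 − r²). If age and log weight correlate at 0.8 to 0.95 (assumed), the factor is 1.7 to 3.2. At n = 18 and SDw = 0.55, the SE goes from 0.12 to about 0.21-0.40.

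**Why n is an upper limit.** CL/F needs a terminal slope from at least 3 points with Rsq of at least 0.8, and post-dose values below quantitation are set to missing (SAP 13.1.1, 13.1.2). Children of 20 kg or less are sampled at 1, 2, 4, 8 and 24 h. With a half-life of 2-3 h and Cmax of 758-1343 ng/mL, simple exponential decay from a peak at 1.5-4 h puts the 24 h value at about 0.3-13 ng/mL. The quantitation limit is not given. If that sample is lost, a child who peaks at 2 h or later has at most two samples after the peak.

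**The case against.** The strongest reply is that section 16 only tidies this report's outputs. Most of the readable items in its list are summaries, tables or listings, and 13.1.4 had already sent population PK elsewhere. On that reading the entry is poor wording and the separate report is still to come. This is plausible and cannot be excluded.

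A reader might therefore go too far in three ways.
- That the SAP cancels the analysis on a ground that cannot apply. The section offers two grounds without assigning them, and 13.1.4 still promises the report. The documents support an unreconciled contradiction, not a proven cancellation.
- That only un-normalised results in three age classes remain, so the endpoint is lost. SAP 13.1.3 also gives an overall summary and by-subject listings, and 13.1.2 allows compartmental analysis and further parameters. Apparent clearance and volume are still estimated, and age is still described by class.
- That Table 1 shows what this trial will find. Its pediatric values are predictions from a model that already contains weight. They show why the check is worth making, not its result.

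It also stands that a weight-plus-age regression may be too imprecise to separate the two at Stage 1 size. And if the population analysis is reported separately, the extra tables are not needed. What survives is the contradiction, and the gap on body size if section 16 is taken at its word.

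**Conclusion.** The point holds as a conflict between SAP section 16 on one side and SAP 13.1.4 and Protocol 10.10 on the other. Neither stated ground explains not doing the analysis. If section 16 governs, the loss is the body-size assessment, not the clearance and volume endpoint. On the protocol's own predictions, the remaining age-class table would hide a 31.5% fall in CL/F per kg within its youngest class and a 48.4% fall by 6-11 years.

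These percentages assume dosing at exactly 2 mg/kg and take Table 1 as given. The slope SE of about 0.10-0.17 at n = 18 is a best case: weight only, assumed SDs, and every subject with an estimable CL/F. The primary endpoint is unaffected. The matter should be corrected, since the remedy is cheap and the samples are already part of the plan.

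**What to change.** Reconcile SAP 13.1.4 with section 16 in one of two ways.
1. Remove population PK from the section 16 list and say there that it is reported separately under 13.1.4. Nothing more is then needed.
2. If it really is dropped, give the reason specific to it and amend 13.1.4 to match. In 13.1.3, add summaries of CL/F in L/h/kg and Vz/F in L/kg, and regressions of log CL/F and log Vz/F on log weight, with slopes and 95% CIs, in subjects whose parameters can be estimated. State how many subjects at or below 20 kg lack an estimate. Enter age only as a secondary addition, because it is collinear with weight.

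The cost is SAP wording and, under the second option, a small amount of extra analysis on data already collected. No study procedure changes.

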6.21.2. Second Primary Malignancies

Second primary malignancies (SPMs) will be monitored as events of interest and should be included as part of the assessment of AEs throughout the course of the study. Investigators are to report any SPM as SAEs regardless of causal relationship to lenalidomide, occurring at any time for the duration of the study, from the time of signing the ICF/IAF until all subjects have been followed for up to 5 years from the last subject's first dose, unless consent is withdrawn, the subject is lost to follow-up or dies. Events of SPM are to be reported using the SAE report form and must be considered an "Important Medical Event" even if no other serious criteria apply; these events must also be documented in the appropriate page(s) of the CRF and subject's source documents. Documentation on the diagnosis of the SPM must be provided at the time of reporting as a SAE (eg, any confirmatory histology or cytology results, X-rays, computed tomography [CT] scans, etc.).

Information about common side effects already known about lenalidomide will be included in the subject informed consent form and should be discussed with the subject as needed during the study. This information can also be found in the Investigator's Brochure (IB) or will be communicated between IB updates in the form of Investigator notifications.

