11.1. Adverse Events

Adverse Events will be coded according to MedDRA dictionary version 18.0 or higher. The severity of AEs will be graded according to the National Cancer Institute Common Terminology Criteria for Adverse Events (NCI CTCAE) (version 4.03, May 2009), except for tumor flare reaction, which is defined using CTCAE version 3.

All AEs will be recorded by the Investigator from the time the subject signs the ICF/IAF until 28 days after the last dose of lenalidomide and those SAEs made known to the Investigator at any time thereafter that are suspected of being related to lenalidomide.

In the occurrence of partial dates, refer to Appendix 18.4 where the date imputation guideline is located.

Treatment-emergent adverse events (TEAEs) are defined as any AE occurring or worsening on or after the first treatment of the IP and within 28 days after the last dose administration date. All TEAEs, AEs leading to IP discontinuation, AEs leading to dose reduction/ interruption, AEs related to lenalidomide, and SAEs and AEs leading to death will be summarized by cycle up to a 28-day period after last cycle (see section 5.2), as well as by subject worst recorded grade per event type, SOC, PT and grade. A summary of AEs with NCI CTCAE v 4.0 Grade 3 or higher (except for tumor flare reaction, which is defined using CTCAE version 3), as well as the most frequent PTs, will also be provided by grade and PT. If a subject experiences the same AE more than once with different severity grade, then the event with the highest grade will be tabulated in “by grade” tables. If a subject experiences multiple AEs under the same PT/SOC, then the subject will be counted only once for that PT/SOC. In addition, AEs with a missing intensity will be presented in the summary table as an intensity category of “Missing”.

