11.3. Second Primary Malignancy

Second primary malignancies are any occurring regardless of relationship to study drug during the conduct of the study including up to 5 years after last subject first dose date.

Events of SPMs will be tabulated for the following categories:

- All SPMs (invasive and non-invasive SPMs)
- All invasive SPMs (hematologic and solid tumor SPMs)
- All hematologic SPMs (AML, myelodysplastic syndromes (MDS), MDS to AML (for MDS events that transform to AML), B-cell malignancies, and other hematologic cancers)
- All solid tumor SPMs
- All non-invasive SPMs (non-melanoma skin cancers)

For each of the above SPM categories, SPMs will be further tabulated using the MedDRA preferred term. Each subject is counted only once within each SPM category as well as within each preferred term.

Additionally, the number and percentage of subjects with SPMs who died and those who did not die will be tabulated by SPM category.

It should be noted that these analyses with regard to SPMs are based on the number of subjects with at least one SPM and not the total number of SPMs.

For each SPM category, time to onset will be calculated as time (in months) from the start of the study treatment to the onset of the SPM for each affected subject. For the subjects with more than one new malignancy within an SPM category, the onset of the earliest SPM will be used. Time to onset will be summarized descriptively for each SPM category [mean, median, Standard Deviation (StdDev), first quartile (Q1), third quartile (Q3), minimum (Min), and maximum (Max)].

A scatter plot to graphically display the time to onset of hematologic and solid tumor SPMs for each SPM by dose level will be provided.

For each SPM category, the incidence rate per 100 person-years will be calculated as: (the number of subjects with any SPM in the SPM category/total person-years)*100. Total person-years are defined as the total time from the date of first treatment to the first onset date of the specified SPM for subjects with the specified SPM plus the total time from the date of first treatment to the date of the last follow-up or death for subjects without the specified SPM. Incidence rates per 100 person-years and the 95% confidence intervals will be calculated for each treatment arm and SPM category. Confidence interval at 95% level for the incidence rate per 100 person-years is calculated as follows: $\text{incidence rate} * \exp\{\pm 1.96 * n^{(-1/2)}\}$.

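### SAP 16 drops every dedicated second-primary-malignancy output with no time limit, so SPMs arising more than 28 days after the last dose get no all-causality count, person-time or rate at study end

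*SAP*

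**What the plan says.** **Collection.** Protocol 6.21.2 is explicit on causality: "Investigators are to report any SPM as SAEs regardless of causal relationship to lenalidomide". Reporting runs from consent until five years after the last subject's first dose. In Protocol Table 2, general adverse event collection stops at the 28-day visit, while SPM assessment continues for the five years.

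**Planned analysis.** SAP 11.3 uses the same window: "Second primary malignancies are any occurring regardless of relationship to study drug during the conduct of the study including up to 5 years" after the last subject's first dose. It plans tables by SPM category, time to onset, a scatter plot and incidence rates: "Incidence rates per 100 person-years and the 95% confidence intervals will be calculated for each treatment arm and SPM category". The interval is the rate multiplied by exp(±1.96·n^(-1/2)). The section ends by saying that the sponsor will produce the SPM listings.

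**Cancellation.** SAP 16 lists analyses that will not be conducted, "due to a low (1 or fewer) number of subjects reporting certain measurements or to redundant presentation". One entry is "Second primary malignancy related tables, listings and figures". SAP 16 does not say which of the two reasons applies to SPM, and it sets no time limit.

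**Study end.** SAP 15 says of the final analysis: "For the end of study final analysis, all outputs will be rerun once all subjects will have discontinued the follow-up period".

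**The concern.** The decision to drop the SPM outputs rests on what had been seen during the study, but SPM collection continues for years afterwards. A count of 0 or 1 at the time of the decision cannot settle what later follow-up will show. SAP 15 reruns the outputs at study end, and nothing in SAP 15 or 16 restores those that were cancelled.

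The protocol names SPM as a specific safety concern and asks sites and families for long-term follow-up of it in children. For a rare harm, no events in a known amount of person-time, with an upper limit, is a result in its own right. As written, the SAP commits to no such statement.

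There is also a plain conflict of instructions. SAP 11.3 tells the programmer to produce SPM tables and the sponsor to produce SPM listings, and SAP 16 says neither will be done.

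**Working it through.** The documents give no SPM count, rate or person-years, so there is no plan figure to reproduce. The check has three parts.

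**1. What still captures an SPM if SAP 16 is followed as written**

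- *Special-interest tables (SAP 11.1.3).* SPM remains a category. SAP 16 drops the drug-related tables, the serious-related and serious-leading-to-discontinuation tables, and the maximum-intensity tables. It does not name the by-category, all-TEAE, grade 3/4 or serious tables. These cover TEAEs only, and SAP 11.1 defines a TEAE as starting or worsening on treatment or "within 28 days after the last dose administration date". A later SPM is outside them.
- *Listings of AEs, SAEs and special-interest SAEs (SAP 11.1.2).* These are retained. A late SPM reported as an SAE can appear as a row, without person-time.
- *Table of non-treatment-emergent AEs (SAP 11.1.2).* This is retained. It might show a late SPM, but its window is not defined for this purpose and it gives no rate.
- *Drug-related SAEs over the whole follow-up (SAP 11).* These are retained, so a late SPM suspected to be related is reported. One judged unrelated is not covered by this commitment.
- *Deaths by cause in follow-up (SAP 11.2).* These are retained, but are informative only for a fatal SPM.

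Person-years and incidence rates for SPM are specified only in SAP 11.3, which SAP 16 cancels.

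**2. The SAP 11.3 interval at the counts SAP 16 mentions**

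SAP 11.3 does not define n beside the formula. It is read here as the number of subjects with an SPM in the category.

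- Planned limits on the event scale: n·exp(−1.96/√n) to n·exp(+1.96/√n).
- Exact Poisson limits: χ²(0.025; 2n)/2 to χ²(0.975; 2n+2)/2, with lower limit 0 at n = 0.

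| n | Planned formula | Exact Poisson |
|---|---|---|
| 0 | undefined (division by zero) | 0 to 3.69 |
| 1 | 0.14 to 7.10 | 0.025 to 5.57 |
| 2 | 0.50 to 8.00 | 0.24 to 7.22 |

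At n = 1 these limits are also multiples of the rate. The formula gives no upper bound at zero events and approximates poorly at one.

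**3. What a zero-event result would say**

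The exact upper limit per 100 person-years is 100 × 3.689 / PY. Mean follow-up per subject is not stated, so a range is assumed. The documents give 43 evaluable subjects for the full study and 18 for Stage 1.

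| Assumed mean follow-up (years) | 43 subjects: PY | Upper limit | 18 subjects: PY | Upper limit |
|---|---|---|---|---|
| 0.5 | 21.5 | 17.2 | 9 | 41.0 |
| 1 | 43 | 8.6 | 18 | 20.5 |
| 2 | 86 | 4.3 | 36 | 10.2 |
| 5 | 215 | 1.7 | 90 | 4.1 |

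**The case against.** A reader might infer from SAP 16 that SPMs will go unreported. The documents do not support that, because the routes in part 1 of the check remain open and every SPM is an SAE by protocol definition. The loss is confined to the late, all-causality summary, and it bears most on SPMs judged unrelated.

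A reader might also take SPM to be the only reason for the five-year follow-up, or think that a protocol-specified analysis has been removed. Neither holds. Protocol 6.23 also follows drug-related SAEs, new anticancer therapy and HSCT. SPM is not a listed secondary endpoint, and the visible text of Protocol 10.7 has no separate SPM analysis.

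The stated reasons deserve a fair hearing. With 0 or 1 subjects, dropping five category tables, onset quartiles and a scatter plot is ordinary practice. Redundancy is a plausible reason for treatment-emergent SPMs, which also appear among the special-interest events. It does not explain dropping person-time and rates, which appear nowhere else. Nor can a low count seen part-way through speak for follow-up still to come.

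It could be argued that SAP 15 restores the outputs, since "all outputs will be rerun once all subjects will have discontinued the follow-up period". The more natural reading is that the rerun covers the outputs that remain after SAP 16. If the sponsor intends otherwise, the text should say so.

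The interval problem is dormant while SAP 11.3 stays cancelled, and matters only if a rate is reported. That zero is the likeliest count is not stated anywhere: SAP 16 says 1 or fewer for unspecified measurements. Finally, with short follow-up the upper limit would be wide and would rule out little.

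**Conclusion.** The point holds in a limited form. SAP 16 cancels the dedicated SPM outputs without restricting this to the primary final analysis, and it conflicts with SAP 11.3. Followed as written, an SPM arising more than 28 days after the last dose and judged unrelated gets at most a row in a listing or in a general table, with no SPM count, person-time or rate.

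The primary endpoint and the activity conclusion are untouched. The effect is on how the long-term safety data are reported. The gain from correcting it depends on person-years that the documents do not give. Under the assumed range, a zero-event result would bound the rate at about 17.2 to 1.7 per 100 person-years for 43 subjects, or 41.0 to 4.1 for 18. That ranges from little information to a usable bound. Given the low cost, the change should be made.

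**What to change.** 1. In SAP 16, limit the SPM entry to the primary final analysis and state which of the two reasons applies.
2. Reconcile it with SAP 11.3, including whether the sponsor's SPM listings will still be produced.
3. For the end-of-study analysis, commit to one table giving the number of subjects with any SPM, total person-years, and the rate with an exact Poisson 95% interval for the single arm. Add one SPM listing covering all causalities. The category tables, onset quartiles and scatter plot need not return if the count stays at 0 or 1.
4. In SAP 11.3, replace the exponential formula with the exact interval, define n, and remove the reference to treatment arms.

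The cost is one small table and one listing from data already being collected. The drawback is an upper limit that may be wide, which reporting the person-years beside it makes plain.
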